**Panel 10: Beta mix components for the prior distribution for IGA-CHE vehicle responders from LP0133-1401 and LP0133-1402**

	Component 1	Component 2	Component 3	Component 4	Robust
W	0.42	0.28	0.06	0.04	0.20
A	16.36	3.44	5.86	1.16	1.00
B	180.23	39.78	35.60	5.07	1.00

**Note:** Not rounded data can be found in /leo/clinical/lp0133/1426/stat/sap/rob\_viga.xpt.

**Panel 11: Beta mix components for the prior distribution for IGA-CHE delgocitinib 20 mg/g responders from LP0133-1401 and LP0133-1402**

	Component 1	Component 2	Component 3	Component 4	Robust
W	0.38	0.16	0.13	0.12	0.20
A	21.30	6.35	1.55	14.15	1.00
B	66.59	30.83	3.26	27.17	1.00

**Note:** Not rounded data can be found in /leo/clinical/lp0133/1426/stat/sap/rob\_diga.xpt.

THIS DOCUMENT CONTAINS CONFIDENTIAL INFORMATION AND MUST NOT BE COPIED OR MADE AVAILABLE TO ANY THIRD PARTY WITHOUT THE PRIOR WRITTEN CONSENT OF THE LEO PHARMA GROUP

Once the trial is unblinded the posterior distributions for the proportion of responders for vehicle and delgocitinib 20 mg/g for IGA-CHE given the robust mixture priors can be calculated with the 'postmix' function in the statistical package 'RBesT'.

The conclusion on treatment effect will be based on the calculated difference (based on 1.000.000 samples) in the posterior distributions. A statistically significant treatment effect is concluded if the probability that the difference (delgocitinib cream 20 mg/g minus cream vehicle) is larger than zero, is larger than 0.975. That is if  $P(\text{delgocitinib cream 20 mg/g} - \text{cream vehicle} > 0) > 0.975$ . The 95% credibility interval (generated as the 2.5% and 97.5% quantiles of the difference in posterior distributions) will be presented along with the mean and median.

#### 5.5.1.8 Binary key secondary endpoints analyses using the primary estimand, Bayesian approach

The Bayesian analyses of the primary estimand for the key secondary endpoints will be performed in a similar manner as for the primary endpoint IGA-CHE. The various number of responders and beta mix components for vehicle and delgocitinib 20 mg/g can be found in the following subsections.

The prior for the between-trial heterogeneity  $\tau$  is set to 0.5 and the prior for the weight on the non-informative part of the prior is set to 0.2 for all key secondary endpoints.

As for the Bayesian approach of the primary endpoint analysis using the primary estimand the prior distributions for the key secondary endpoints shown in the SAP are fixed and will not change after un-blinding.

##### 5.5.1.8.1 HECSI-90 responders

#### Panel 12: HECSI-90 responders from LP0133-1273, LP0133-1401 and LP0133-1402

	LP0133-1401 a		LP0133-1402 b		LP0133-1273 c	
	Vehicle	Delgocitinib 20 mg/g	Vehicle	Delgocitinib 20 mg/g	Vehicle	Delgocitinib 20 mg/g
Responders	20	96	14	97	5	12
Total	162	325	159	313	38	41

**Notes:** **a** = 1401 numbers are from final\_20230308, t\_20240\_hecsi90\_byvis.txt., **b** = 1402 numbers are from final\_20230324, t\_20240\_hecsi90\_byvis.txt., **c** = 1273 numbers are from exploratory/output, t\_60072\_hecsi90\_cmh\_iga34\_fas.txt.

THIS DOCUMENT CONTAINS CONFIDENTIAL INFORMATION AND MUST NOT BE COPIED OR MADE AVAILABLE TO ANY THIRD PARTY WITHOUT THE PRIOR WRITTEN CONSENT OF THE LEO PHARMA GROUP

**Panel 13: Beta mix components for the prior distribution for HECSI-90 vehicle responders from LP0133-1273, LP0133-1401 and LP0133-1402**

	Component 1	Component 2	Component 3	Component 4	Robust
W	0.43	0.24	0.07	0.06	0.20
A	25.96	7.22	16.14	1.46	1.00
B	211.47	69.47	80.24	7.16	1.00

**Note:** Not rounded data can be found in /leo/clinical/lp0133/1426/stat/sap/rob\_vh90.xpt.

**Panel 14: Beta mix components for the prior distribution for HECSI-90 delgocitinib 20 mg/g responders from LP0133-1273, LP0133-1401 and LP0133-1402**

	Component 1	Component 2	Component 3	Component 4	Robust
W	0.45	0.27	0.08		0.20
A	106.68	14.57	3.01		1.00
B	246.79	33.77	6.07		1.00

**Note:** Not rounded data can be found in /leo/clinical/lp0133/1426/stat/sap/rob\_dh90.xpt.

**5.5.1.8.2 HESD itch  $\geq$  4-point reduction responders**

**Panel 15: HESD itch  $\geq$  4-point reduction responders from LP0133-1273, LP0133-1401 and LP0133-1402**

	LP0133-1401 a		LP0133-1402 b		LP0133-1273 c	
	Vehicle	Delgocitinib 20 mg/g	Vehicle	Delgocitinib 20 mg/g	Vehicle	Delgocitinib 20 mg/g
Responders	37	152	31	146	4	14
Total	161	323	156	309	24	26

**Notes:** **a** = 1401 numbers are from final\_20230308, t\_20520\_hesd\_itchr4\_byvis.txt, **b** = 1402 numbers are from final\_20230324, t\_20520\_hesd\_itchr4\_byvis.txt, **c** = 1273 numbers are from efficacy/output, t\_20230\_hesd\_pruri\_cmh\_fas.txt.

**Panel 16: Beta mix components for the prior distribution for HESD itch  $\geq$  4-point reduction vehicle responders from LP0133-1273, LP0133-1401 and LP0133-1402**

	Component 1	Component 2	Component 3	Component 4	Robust
W	0.47	0.13	0.12	0.09	0.20
A	42.15	19.75	11.67	2.05	1.00
B	159.56	57.20	61.56	6.17	1.00

**Note:** Not rounded data can be found in /leo/clinical/lp0133/1426/stat/sap/rob\_vitc.xpt.

THIS DOCUMENT CONTAINS CONFIDENTIAL INFORMATION AND MUST NOT BE COPIED OR MADE AVAILABLE TO ANY THIRD PARTY WITHOUT THE PRIOR WRITTEN CONSENT OF THE LEO PHARMA GROUP

**Panel 17: Beta mix components for the prior distribution for HESD itch  $\geq$  4-point reduction delgocitinib 20 mg/g responders from LP0133-1273, LP0133-1401 and LP0133-1402**

	Component 1	Component 2	Component 3	Component 4	Robust
W	0.37	0.21	0.15	0.07	0.20
A	135.80	85.18	7.10	7.02	1.00
B	154.36	87.39	6.75	9.26	1.00

**Note:** Not rounded data can be found in /leo/clinical/lp0133/1426/stat/sap/rob\_dite.xpt.

**5.5.1.8.3 HESD pain  $\geq$  4-point reduction responders**

**Panel 18: HESD pain  $\geq$  4-point reduction responders from LP0133-1273, LP0133-1401 and LP0133-1402**

	LP0133-1401 a		LP0133-1402 b		LP0133-1273 c	
	Vehicle	Delgocitinib 20 mg/g	Vehicle	Delgocitinib 20 mg/g	Vehicle	Delgocitinib 20 mg/g
Responders	41	143	32	143	1	14
Total	149	291	141	294	15	20

**Notes:** **a** = 1401 numbers are from final\_20230308, t\_20630\_hesd\_painr4\_byvis.txt, **b** = 1402 numbers are from final\_20230324, t\_20630\_hesd\_painr4\_byvis.txt, **c** = 1273 numbers are from exploratory/output, t\_70014\_pain4\_modsev.txt.

**Panel 19: Beta mix components for the prior distribution for HESD pain  $\geq$  4-point reduction vehicle responders from LP0133-1273, LP0133-1401 and LP0133-1402**

	Component 1	Component 2	Component 3	Component 4	Robust
W	0.34	0.33	0.13		0.20
A	5.34	36.96	1.67		1.00
B	18.89	117.43	4.82		1.00

**Note:** Not rounded data can be found in /leo/clinical/lp0133/1426/stat/sap/rob\_vpai.xpt.

**Panel 20: Beta mix components for the prior distribution for HESD pain  $\geq$  4-point reduction delgocitinib 20 mg/g responders from LP0133-1273, LP0133-1401 and LP0133-1402**

	Component 1	Component 2	Component 3	Component 4	Robust
W	0.35	0.35	0.10		0.20
A	12.16	123.97	2.53		1.00
B	11.04	124.54	1.94		1.00

**Note:** Not rounded data can be found in /leo/clinical/lp0133/1426/stat/sap/rob\_dpai.xpt.

THIS DOCUMENT CONTAINS CONFIDENTIAL INFORMATION AND MUST NOT BE COPIED OR MADE AVAILABLE TO ANY THIRD PARTY WITHOUT THE PRIOR WRITTEN CONSENT OF THE LEO PHARMA GROUP

#### 5.5.1.8.4 HESD total score $\geq$ 4-point reduction responders

##### Panel 21: HESD total score $\geq$ 4-point reduction responders from LP0133-1273, LP0133-1401 and LP0133-1402

	LP0133-1401 a		LP0133-1402 b		LP0133-1273 c	
	Vehicle	Delgocitinib 20 mg/g	Vehicle	Delgocitinib 20 mg/g	Vehicle	Delgocitinib 20 mg/g
Responders	38	146	32	137	2	10
Total	156	309	153	308	24	27

**Notes:** **a** = 1401 numbers are from final\_20230308, t\_20400\_hesdr4\_byvis.txt, **b** = 1402 numbers are from final\_20230324, t\_20400\_hesdr4\_byvis.txt, **c** = 1273 numbers are from exploratory/output, t\_70017\_comp4\_modsev.txt.

##### Panel 22: Beta mix components for the prior distribution for HESD total score $\geq$ 4-point reduction vehicle responders from LP0133-1273, LP0133-1401 and LP0133-1402

	Component 1	Component 2	Component 3	Component 4	Robust
W	0.37	0.31	0.12		0.20
A	33.12	5.26	1.72		1.00
B	122.77	21.36	5.48		1.00

**Note:** Not rounded data can be found in /leo/clinical/lp0133/1426/stat/sap/rob\_vhes.xpt.

##### Panel 23: Beta mix components for the prior distribution for HESD total score $\geq$ 4-point reduction delgocitinib 20 mg/g responders from LP0133-1273, LP0133-1401 and LP0133-1402

	Component 1	Component 2	Component 3	Component 4	Robust
W	0.34	0.23	0.16	0.07	0.20
A	128.18	58.31	6.89	4.79	1.00
B	149.81	76.14	7.44	8.13	1.00

**Note:** Not rounded data can be found in /leo/clinical/lp0133/1426/stat/sap/rob\_dhes.xpt.

#### 5.5.1.9 Sensitivity analysis of the chosen between-trial heterogeneity $\tau$ and the weight on the non-informative part of the prior, Bayesian approach

Once the trial is unblinded sensitivity analyses will be performed for the primary endpoint and all key secondary endpoints in order to evaluate the influence of the prespecified selected prior for  $\tau$  and the prespecified selected prior weight parameter for the non-informative part of the prior.

THIS DOCUMENT CONTAINS CONFIDENTIAL INFORMATION AND MUST NOT BE COPIED OR MADE AVAILABLE TO ANY THIRD PARTY WITHOUT THE PRIOR WRITTEN CONSENT OF THE LEO PHARMA GROUP

The values of the prior for the between-trial heterogeneity  $\tau$  tested are 0.2, 0.3, 0.4, 0.5, 0.75 and 1.0. The values of the weight on the non-informative part of the prior tested are 0 to 1 by 0.1.

### **5.5.2 Primary estimand for continuous endpoints: composite strategy**

This primary estimand evaluates the treatment effect in adolescents with moderate to severe CHE, without initiation of rescue treatment or permanent discontinuation of IMP.

For subjects who received rescue treatment or who have permanently discontinued IMP prior to the endpoint of interest, observed data after the IEs will be imputed by using WOCF (including the baseline value) which is considered an extremely unfavourable value.

#### **5.5.2.1 Definition of continuous endpoints**

The continuous endpoints (secondary and exploratory) to be analysed with the composite strategy estimand are:

- Change in cDLQI score from baseline to Week 16.
- Percentage change in HECSI score from baseline to Weeks 4, 8, and 16.
- Change in HESD itch score (weekly average) from baseline to Weeks 2, 4, 8, and 16.
- Change in HESD pain score (weekly average) from baseline to Weeks 2, 4, 8, and 16.
- Change in HESD score (weekly average) from baseline to Weeks 2, 4, 8, and 16.
- Change in cDLQI score from baseline to Week 4.

#### **5.5.2.2 Analysis of continuous endpoints for the primary estimand**

For subjects who received rescue treatment or who have permanently discontinued IMP prior to the endpoint of interest, observed data after the IEs will be considered non-response by using WOCF (including the baseline value).

Missing data for subjects who do not experience an IE prior to the visit for the endpoint of interest will be imputed as WOCF (including the baseline value). Similarly, missing data at the endpoint of interest for subjects who do experience an IE prior to this visit will be imputed as WOCF (including the baseline value).

The change (or percentage change) from baseline to the endpoint of interest will be analysed using an ANCOVA model with effects of treatment group, baseline IGA-CHE score, and baseline value (endpoint of interest). LSMeans will be estimated using observed margins. The difference in the LSMeans between the treatment groups will be presented along with the corresponding 95% CI and nominal p-value.

THIS DOCUMENT CONTAINS CONFIDENTIAL INFORMATION AND MUST NOT BE COPIED OR MADE AVAILABLE TO ANY THIRD PARTY WITHOUT THE PRIOR WRITTEN CONSENT OF THE LEO PHARMA GROUP

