## **9.3 Treatment assignment and blinding**

### **9.3.1 Treatment assignment**

Subjects who have been found to comply with all the inclusion criteria and not to violate any of the exclusion criteria will be randomised at baseline (Day 1) in a 3:1 ratio to receive treatment with either delgocitinib cream 20 mg/g or cream vehicle. The randomisation will be stratified by baseline IGA-CHE score (3 or 4).

The IRT system will be used to control randomisation and stratification factors, along with IMP supply chain and expiry tracking.

THIS DOCUMENT CONTAINS CONFIDENTIAL INFORMATION AND MUST NOT BE COPIED OR MADE AVAILABLE TO ANY THIRD PARTY WITHOUT THE PRIOR WRITTEN CONSENT OF THE LEO PHARMA GROUP

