### 14.1 Sample size

92 subjects will be randomised 3:1 to delgocitinib cream 20 mg/g or cream vehicle.

Based on response rates from the phase 2b dose-ranging trial in adults (LP0133-1273), a one-sided significance level at 2.5% and a sample size of 92 subjects will provide at least 80% power for detecting a treatment difference in the primary endpoint assuming an IGA-CHE TS response at Week 16 of 40.2% for delgocitinib cream 20 mg/g and 10.5% for cream vehicle.

When the response rates from LP0133-1401 and LP0133-1402 are included in the sample size calculation, this will result in a power which is lower than first anticipated.

The power obtained when using the Bayesian approach on a sample size of 92 subjects is explained in Section [14.3.17](#).

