#### 14.3.17 Description of the Bayesian analyses and design characteristics

The design characteristics is based on 92 randomised subjects (69 in the delgocitinib cream 20 mg/g group and 23 in the cream vehicle group).

For each endpoint, the choice of the between-trial heterogeneity parameter ( $\tau$ ) and the weight on the non-informative part of the prior is described. In addition, the degree of borrowing is described by the ESS and finally, the influence of the type I error and power investigated.

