### 14.3.17.3.1 HECSI-90

The average response rate for cream vehicle on HECSI-90 in the adult trials (LP0133-1273, LP0133-1401 and LP0133-1402) is 10.9% (Panel 36), corresponding to a type I error <5% (Panel 37). The average treatment effect is 19.3% (Panel 36), corresponding to a power >80% (Panel 37).

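### With 69 vs 23 subjects, the ordinary ANCOVA for the continuous endpoints gives mis-sized 95% CIs if the arms' residual SDs differ materially; a variance estimate that allows for this should be prespecified.

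*SAP*

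**What the plan says.** SAP 5.5.2.2 states that the change or percentage change from baseline "will be analysed using an ANCOVA model with effects of treatment group, baseline IGA-CHE score, and baseline value (endpoint of interest". Protocol 14.3.10 specifies the same model. On reporting, the SAP adds: "The difference in the LSMeans between the treatment groups will be presented along with the corresponding 95% CI and nominal p-value".

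Neither document says that a single residual variance is assumed. Neither gives a variance by treatment group, a robust standard error, or any sensitivity analysis for these endpoints: the missing-data sensitivity analyses are confined to the primary endpoint (Protocol 14.3.5.1), and SAP Panel 8 lists one analysis for continuous data. The ordinary ANCOVA with one pooled residual variance is therefore the natural reading. For the binary risk difference, by contrast, SAP 5.5.1.2 names a specific variance estimator.

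On allocation, Protocol 9.3.1 says subjects "will be randomised at baseline (Day 1) in a 3:1 ratio", and Protocol 14.3.17 gives the planned arms as "69 in the delgocitinib cream 20 mg/g group and 23 in the cream vehicle group".

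The endpoints concerned are change in cDLQI to Week 16 (secondary), and percentage change in HECSI, change in the three HESD scores and change in cDLQI to Week 4 (exploratory). Under SAP 2.1, only the Bayesian analyses belong to the testing hierarchy.

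**The concern.** A pooled residual variance gives a correct standard error for the treatment difference when the arms have equal spread. It is also close to correct when the arms are of equal size. A 3:1 split removes that second protection. With equal SDs, the vehicle arm carries (1/23) / (1/23 + 1/69) = 75% of the variance of the difference. Before covariates, however, 68 of the 90 degrees of freedom behind the pooled variance come from delgocitinib. The larger arm thus sets the estimated spread, while the smaller arm drives the uncertainty.

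Unequal spread is plausible. Percentage change in HECSI cannot fall below -100% but can rise with worsening, and cDLQI is bounded at 0 and 30. The WOCF rule can also alter an arm's spread, depending on how many subjects it touches there.

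At stake is the width of the reported CIs, and the nominal p-values that go with them, for one secondary endpoint and a set of exploratory ones.

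**Working it through.** **Inputs.** Arm sizes 69 and 23 (Protocol 14.3.17). Model terms: treatment, baseline IGA-CHE, baseline value (SAP 5.5.2.2). Residual SDs by arm are not given for any continuous endpoint, so the ratio q = vehicle SD / delgocitinib SD is an assumption, varied from 0.5 to 2.0. Adult HECSI-90 rates of 30.2% and 10.9% (Protocol 14.3.17.3.1, Panel 36) are used for illustration only.

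**Step 1: the plan's own figure.** The only frequentist sample-size figure concerns the binary primary endpoint: Protocol 14.1 says "a one-sided significance level at 2.5% and a sample size of 92 subjects will provide at least 80% power", assuming "40.2% for delgocitinib cream 20 mg/g and 10.5% for cream vehicle". The pooled rate is (3 × 0.402 + 0.105)/4 = 0.32775. The null SE is sqrt(0.32775 × 0.67225 × (1/69 + 1/23)) = 0.1130. The alternative SE is sqrt(0.402 × 0.598/69 + 0.105 × 0.895/23) = 0.0870. Then z = (0.297 - 1.96 × 0.1130)/0.0870 = 0.868, which is 80.7% power. The figure reproduces and fits arms of 69 and 23. It says nothing about continuous endpoints, for which the documents give no power, SD or CI width.

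**Step 2: pooled SE against true SE, ignoring covariates.** Set the delgocitinib variance to 1 and the vehicle variance to q².

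- True variance of the difference: 1/69 + q²/23.
- Variance the pooled model reports on average: [(68 + 22q²)/90] × (1/69 + 1/23).
- Multiplying both by 69 gives (model SE / true SE)² = 4(68 + 22q²) / [90(1 + 3q²)].

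At q = 1.25: 4 × 102.375 / (90 × 5.6875) = 0.800, so the SE ratio is 0.89. At q = 1.5: 4 × 117.5 / (90 × 7.75) = 0.674, ratio 0.82. At q = 2: 4 × 156 / (90 × 13) = 0.533, ratio 0.73. At q = 0.8: 4 × 82.08 / (90 × 2.92) = 1.249, ratio 1.12. With equal arm sizes the same ratio is 1 for every q.

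**Step 3: coverage of the planned 95% CI.** The SAP's ANCOVA was simulated with normal errors, with 20,000 trials per setting and again with 6,000. In the larger run, 30% of subjects were assumed to have baseline IGA-CHE 4, outcomes were independent of the baseline covariates, and the t quantile used 88 degrees of freedom.

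| Vehicle/delgocitinib SD | Model SE / true SE | Planned CI, 20,000 | Planned CI, 6,000 | HC3, 20,000 | HC3, 6,000 |
|---|---|---|---|---|---|
| 0.5 | 1.37 | 99.1% | not run | 95.8% | not run |
| 0.67 | 1.22 | 98.1% | 98.1% | 95.6% | 95.5% |
| 0.8 | 1.12 | 97.2% | 97.0% | 95.4% | 95.3% |
| 1.0 | 1.00 | 95.0% | 95.1% | 95.3% | 95.4% |
| 1.25 | 0.89 | 92.0% | 91.6% | 95.1% | 94.6% |
| 1.5 | 0.82 | 89.4% | 89.5% | 95.0% | 95.2% |
| 2.0 | 0.73 | 85.0% | 83.9% | 94.9% | 94.9% |

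**Step 4: can the direction be fixed for percentage change in HECSI?** Four assumed outcome mixtures, each with a working drug, were put through the same ANCOVA. The first and third use the adult HECSI-90 rates.

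| Assumed shape | SD delgocitinib / vehicle | Vehicle/delgocitinib | Planned CI coverage |
|---|---|---|---|
| Adult-like | 41.0 / 43.1 | 1.05 | 94.5% |
| Strong drug effect | 31.6 / 43.1 | 1.36 | 90.7% |
| Drug arm split into responders and non-responders | 48.3 / 43.7 | 0.90 | 95.9% |
| Same drug arm, flatter vehicle arm | 48.3 / 37.5 | 0.78 | 97.3% |

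The direction reverses with the assumed shape.

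**The case against.** The strongest reply is that no defect is demonstrated. Ordinary ANCOVA is a conventional prespecified analysis. The documents give no SDs, so the error has unknown sign and size. The p-values are labelled nominal, and the endpoints are outside the hierarchy. If the drug leaves the outcome distribution unchanged, the spreads are equal and the test keeps its level. All of this stands, and it limits the weight of the point.

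A reader might go further and infer that the CI for percentage change in HECSI will be too narrow, and so overstate precision in the drug's favour, because the vehicle arm keeps more disease. One model does give this: a lognormal remaining fraction with equal log-SD (1.0 to 1.5) in both arms, matched to 30.2% and 10.9%, with worsening capped at +100% or +200%. The vehicle/delgocitinib SD ratio is then 1.28 to 1.73 and coverage is 86% to 92%. But equal log-SDs make the worse arm more variable by construction, and at log-SD 1.5 the model has 38% of vehicle subjects worsening and 22% more than doubling their score. If worsening is capped at zero, the ratio falls to 1.07 to 1.31. A beta-distributed fraction fitted to the same rates gives 0.98 to 1.12. The documents support none of these shapes over the others.

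Nor do they support the inference that WOCF inflates the vehicle arm's spread. It places subjects at baseline or worse, which can be more of an outlier in an arm that mostly improves.

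HC3 is not perfect either: in the skewed lognormal settings it covered 92% to 95%, still better than the planned interval. What the reply does not remove is that, with the direction unknown before unblinding, an SE valid either way is the safer prespecification.

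**Conclusion.** The point holds as a matter of robustness. If residual SDs differ by a factor of about 1.25 or more in either direction, the planned intervals are materially mis-sized. They are conservative when the delgocitinib arm is the more variable, and anti-conservative when the vehicle arm is. At a vehicle/delgocitinib ratio of 1.5, the non-coverage rate is about double the nominal 5%.

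This rests on reading ANCOVA as a single-variance model, on the planned arm sizes, and on assumed SD ratios with normal errors. No direction or size is claimed for any particular endpoint. The consequence is confined to CIs and nominal p-values for secondary and exploratory endpoints. A reader who inferred that the trial's confirmatory result is at risk would be mistaken, since that rests on Bayesian analyses of binary endpoints. The change is worth making but is not a condition for the trial's main conclusions.

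**What to change.** In SAP 5.5.2.2, keep the ANCOVA, its covariates and the LSMeans difference. Add one sentence, before unblinding, stating that the SE, 95% CI and nominal p-value are taken from an HC3 heteroscedasticity-consistent variance (with the residual degrees of freedom), or alternatively from separate residual variances by treatment group with Satterthwaite degrees of freedom. Name one of the two. Because Protocol 14.3.10 describes the plain model, record the change in SAP Section 6.

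The cost is that sentence, the Section 6 entry and one program option. In simulation, HC3 made the CI 2.9% wider when the variances were equal; at a vehicle/delgocitinib SD ratio of 0.67 it made the CI 15% narrower. If the sponsor prefers to keep the ordinary ANCOVA as the main analysis, the robust version should at least be prespecified as a sensitivity analysis. A choice made after unblinding could look driven by the results.

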## 5.6 Supplementary estimand

The following supplementary estimand is defined for the primary binary endpoint.

### 5.6.1 Supplementary estimand for binary primary endpoint: treatment policy strategy, Frequentist approach

The supplementary estimand “Treatment policy” evaluates the treatment effect in adolescents 12-17 years of age with moderate to severe CHE as the risk difference for achieving a response, regardless of initiation of rescue treatment or permanent discontinuation of IMP.

